4.2 Secondary objectives

4.2.1. Clinical recovery during follow-up

The first secondary outcome is time until full clinical recovery (in days) during follow-up (day 1 to day 30).

Null hypothesis: the diagnostic algorithm including a standardised clinical assessment, a POC CRP test and safety netting advice is inferior to usual care in terms of the number of days until subjects reach full clinical recovery

Alternative hypothesis: the diagnostic algorithm including a standardised clinical assessment, a POC CRP test and safety netting advice is not inferior to usual care in terms of the number of days until subjects reach full clinical recovery

- P Children aged 6 months to 12 years of age with an acute illness episode presenting to in-hours general practices or community paediatrics offices
- I **Diagnostic algorithm** including a standardised clinical assessment, a POC CRP test and safety netting advice
- C Diagnosis and treatment/management as per usual care
- O number of days until full clinical recovery
- T This outcome will be checked from the diary (via app for parents) from day 1 until day of full clinical recovery

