8.7 Trial assessments

Assessment by physician

During the first consultation at baseline, a selection of **clinical features** will be assessed and recorded by the physician in the patient's health record and on the e-CRF, **including the clinical decision tree** (clinician's gut feeling, body temperature, dypnoea). **CRP testing** will be conducted as per the **diagnostic algorithm** as described above (See Flowchart).

The physician will be asked to note in the patient's health record and on the e-CRF whether antibiotics were prescribed, whether this was an immediate or delayed prescription. If the decision to prescribe antibiotics diverted from the suggested algorithm in the intervention arm, physicians will be asked to acknowledge this and explain why on the e-CRF.

Any additional care during follow-up will be left at the discretion of the child's physician. We will use a **point-of-care CRP** test which requires 1.5 μ I of capillary blood obtained by finger prick (results within 4 minutes). Clinical features will be recorded before the CRP test is conducted.

Follow-up (app)

Follow-up information for all children will be collected using direct patient/parent contact using a smartphone app. Information regarding the smartphone app as well as instructions on how to install will be handed to children and their parents at the baseline consultation.

The smartphone app will ask parents and/or children about daily symptoms such as body temperature, cough, treatment and whether they consulted a physician or went to the hospital. The daily follow-up will consist of a maximum of 10 short questions which are answered by ticking the appropriate box. Parents will be asked to complete these questions once a day until the symptoms have resolved and the child is considered cured of the acute illness.

Furthermore, the app will ask parents to complete a few quality-of-life items (proxy version of the EQ-5D-Y questionnaire)(24) and two pain scales (Wong Baker FACES Pain Scale, FLACC scale)(25,26) during follow-up. Some items will be requested daily (visual analogue scale of the proxy version of the EQ-5-D and the Wong Baker FACES Pain Scale), whereas other items will be presented weekly and/or until the child is feeling better (all items of the proxy version of the EQ-5D-Y and the FLACC scale). We will ask parents to complete these questions.

Follow-up (patient health record)

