For each of the outcomes stated above the following target difference is important for the key stakeholder groups consulted (e.g. patients, clinician, and healthcare funder): from 30.43% to 22.65%.

Using a 5% significance level (alpha 0.05), an intracluster correlation coefficient (ICC) of 0.063 (based on data from the ERNIE2 study in the exact same population), and power of 90% (beta 0.1), this would require **55 clusters of 50 patients** in both arms, resulting in **5500 children**. Drop-outs are unlikely to be a large problem since there will be only 1 study visit complemented by the collection of follow-up information. Imputation of missing values for patient-and/or parent/legal guardian-reported outcomes (if there are any) will be considered. Other outcomes will be collected in the patient health record of the physician.

R code:

We used the n4props-function in the R package CRTSize, using the following command:

n4props(0.3043,0.2265,50,0.063, alpha = 0.05, power=0.9, AR=1, two.tailed=TRUE, digits=3)

Considering the pragmatic nature of this trial and in correspondence with the 10% of practices performing nonconsecutive inclusion of patients (high risk of selection bias) during the ERNIE2 trial, we will perform sensitivity analyses only considering physicians who have recruited a minimum of 10 patients per year. Taking into account the required sample size for this analysis of the primary study outcome as part of the sensitivity analysis, these assumptions result in a total sample size of 6111 patients for the primary study outcome.

Secondary outcomes

To demonstrate non-inferiority in the effect of the diagnostic algorithm including the **clinical decision tree**, **POC CRP test and safety netting advice** on the **secondary outcomes**, we use the following assumptions (based on observed proportions in previous trials in children) (11,27):

Secondary outcome		Proportion in intervention group	Proportion in usual care group	Means + pooled standard deviation (SD)	Clinically significant change*
1.	Time to clinical recovery (days)	NA	NA	Mean intervention group: 4.06 Mean usual care group: 4.15 Pooled SD: 3.89	1
2.	Additional investigations at index and/or during follow-up (%)	9.0%	9.8%	NA	3%
3.	Re-consultations during follow-up (%)	33%	34%	NA	4%
4.	Antibiotic prescribing rate during follow up (%)	7%	8%	NA	2%

* based on consensus from a group of clinical researchers with experience in diagnostic and clinical research

NA: not applicable

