Drop-outs are unlikely to be a large problem since there will be only one study visit complemented by the collection of follow-up information.

We will analyse the whole population for the primary analysis and perform a sensitivity analysis excluding the low recruiting practices (less than 10 patients recruited for 12 months) to avoid our results to be susceptible to selection bias. In previous trials this resulted in approximately 10% of practices.

Practices that do not recruit children at all will be stopped after the first two monitoring visits and replaced by new practices to avoid reducing the total number of clusters available for analysis.

The percentage of missing data for the primary outcome of antibiotic prescribing proportion is expected to be low as this will be registered at the first contact consultation. In our previous ERNIE2 trial, we found 4% of missing data for the primary outcome of antibiotic prescribing proportion. Multiple imputation will be considered for the primary outcome measure as well as missing values for patient-reported outcomes (if there are any). Other outcomes will be collected from the patient health record of the physician.

Multiple imputation will be applied to deal with missing data. Imputation will be performed for the binary outcome variable and logistic regression will be used as imputation model. Predictors for the imputation model are baseline patient characteristics and intervention.

2. ARON App Data

A substantial drop-out rate in app completion is anticipated, with non-completion of the app not considered grounds for exclusion from the study. To address this, proactive measures were introduced to enhance participation rates, such as the provision of information about the smartphone app and instructions on installation to children and their parents during the baseline consultation. Additionally, the app was made available in three languages (Dutch, French, English).

Multiple imputation will be applied to deal with missing data. For imputation of continuous variables, a linear regression model will be employed, with baseline patient characteristics and intervention serving as predictors for the imputation model.

3. Administrative Data

Multiple imputation, following Rubin's rules, will be utilized to address missing data. Predictors for the imputation model will include baseline patient characteristics and the intervention.

4. Interview Transcripts

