Null hypothesis. The diagnostic algorithm including a standardized clinical assessment, a POC CRP test and safety netting advice is inferior to usual care in terms of the number of days until subjects reach full clinical recovery.

Analysis. We will conduct a descriptive analysis to determine the median time to recovery for each randomization group. IQR will also be provided for each group.

For graphical representation, Kaplan-Meier curves will be generated. These curves will be used in combination with a log-rank test to compare the survival curves of the randomization groups.

Additionally, will employ a mixed-effects Cox regression model to address clustering at the practice level. The child's age and study arm will be included as predefined covariates in the model. Hazard ratios, along with their corresponding 95% confidence intervals, will be reported.

Exploratory endpoints – Proportional measures

We will provide a descriptive analysis of the proportion of subjects with the outcome of interest for each randomization group.

A mixed-effects logistic regression model will be employed to address clustering at the practice level. The child's age and study arm will be included as predefined covariates in the model. Odds ratios, along with their corresponding 95% confidence intervals will be reported.

••

Exploratory endpoints – Satisfactory measures

Statistical analysis not applicable due to the qualitative nature of the data.

Upon transcription of the interviews verbatim, an inductive thematic analysis approach is employed to analyse the data. The entire data analysis process was facilitated using qualitative data analysis software QSR NVIVO software version 12 (QSR International Pty Ltd, Melbourne, Australia).

Findings will be centred on main themes and subthemes closely aligned with the research inquiries and reflective of the interview content. In addition, illustrative quotes will be included.

Exploratory endpoints - Cost-effectiveness of the intervention

Different types of economic evaluations will be conducted to compare participants in the intervention group with those in the control group:

- **Costing study** to comprehend the overall cost structure, identify significant cost drivers, and compare the cost impact.

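### The SAP's linear-regression imputation of app data does not exempt days to recovery and sits beside a survival analysis with no censoring rule, so imputed recoveries could precede recorded ill days

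*SAP*

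**What the plan says.** Protocol 4.2.1 makes time to full recovery, in days, the first secondary outcome, with a non-inferiority hypothesis. Its source is the parent diary: "This outcome will be checked from the diary (via app for parents) from day 1 until day of full clinical recovery". Protocol 8.7 adds that entries end by design when the child is well: "Parents will be asked to complete these questions once a day until the symptoms have resolved".

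The SAP, under Handling of missing values and other data conventions, 2. ARON App Data, expects many incomplete diaries: "A substantial drop-out rate in app completion is anticipated, with non-completion of the app not considered grounds for exclusion from the study". It then commits to multiple imputation of app data, with this model: "For imputation of continuous variables, a linear regression model will be employed, with baseline patient characteristics and intervention serving as predictors for the imputation model". The diary days a family has already entered are not among the predictors, and no lower limit is set.

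The SAP's analysis of recovery time gives medians and IQRs by arm. It continues "For graphical representation, Kaplan-Meier curves will be generated", adds a log-rank test, and "will employ a mixed-effects Cox regression model to address clustering at the practice level", reporting hazard ratios.

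Protocol 11.1.1 sets the decision rule in days: the upper limit of the 95% confidence interval for intervention minus control must lie below 1 day. Its planning values are an intervention mean of 4.06 and "Mean usual care group: 4.15 Pooled SD: 3.89".

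**The concern.** A family that enters ill days up to day 5 and then stops has told the trial something definite: recovery came after day 5. A survival analysis uses this by right-censoring. The imputation model as written discards it. That model is fitted to children whose recovery was seen before the diary stopped, who are disproportionately early recoverers, and it would give their distribution to children known to have been ill for longer.

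Three things are left open. The app-data rule and the survival analysis are not reconciled, because if every missing recovery time is filled in first, little remains to censor. Neither document says at what day, or whether, an unfinished diary is censored. And because diaries are meant to end at recovery, a rule is needed to tell a cured child from an abandoned diary, and none is given.

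Protocol 4.1 asks that any fall in prescribing be read alongside the secondary outcomes, with the child's well-being in mind. Recovery time is the first of these, so its handling bears directly on that safeguard.

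**Working it through.** **1. The plan's own figure.** For non-inferiority of means, total n = 4 × SD² × (z₁₋α + z₁₋β)² / margin². With SD 3.89, margin 1, true difference 0, one-sided α 0.0125 and power 0.80, this is 4 × 15.13 × (2.241 + 0.842)² = 575.3. Multiplied by the design effect of 2.225 it gives 1280. Both figures in Protocol 11.1.1 (575 and 1280) reproduce, so recovery was planned as a comparison of means in days.

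**2. Impossible and contradictory values.** A linear-regression draw at the usual-care mean and the pooled SD is normal, so P(draw < d) = Φ((d − 4.15)/3.89). Age and gender predictors would shift this only as far as they explain recovery.

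| d (days) | (d − 4.15)/3.89 | P(draw < d) |
|---|---|---|
| 0 | −1.067 | 14% |
| 1 | −0.810 | 21% |
| 3 | −0.296 | 38% |
| 5 | 0.219 | 59% |
| 7 | 0.733 | 77% |

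These follow from the stated model and planning values. They do not depend on any effect between arms.

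**3. Effect on the difference in days.** The documents give no stopping rate and no distribution, so both are assumed here. Take gamma recovery times with true means 4.15 and 5.15 (a harm equal to the margin) and a constant stopping hazard h per day. Recoveries seen before stopping are then gamma with the same shape k and with h added to the rate, so their mean is k/(k/μ + h). Imputing on arm carries the difference between these observed means into the completed data.

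- Usual care: k = (4.15/3.89)² = 1.138 and k/μ = 0.274. The observed mean is 3.51 at h = 0.05 and 3.04 at h = 0.10.
- Slower arm with the same SD of 3.89: k = (5.15/3.89)² = 1.753 and k/μ = 0.340. The observed means are 4.49 and 3.98, so the differences are 0.98 and 0.94 day.
- Slower arm with the same coefficient of variation (SD 3.89 × 5.15/4.15 = 4.83): k = 1.138 and k/μ = 0.221. The observed means are 4.20 and 3.55, so the differences are 0.69 and 0.50 day.

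**4. Effect on the non-inferiority decision.** The simulation used 122 practices of 57 children, ICC 0.025, SD 3.89 in both arms, whole-day recovery times, 10 imputations combined by Rubin's rules, and the 95% interval against 1 day. There were 150 to 300 runs per scenario, so simulation error is about 1 to 4 percentage points. At a nominal true slowing of 1 day (about 0.98 after rounding), complete data declared non-inferiority in about 2–5% of runs.

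| Diaries stopping per day | Recovery missing | Difference, linear imputation | Declared non-inferior | Difference, imputing only beyond last ill day |
|---|---|---|---|---|
| 5% | 22% | 0.95 | 8–9% | 0.97 |
| 10% | 38% | 0.91 | 18–19% | 0.99 |
| 20% | 59% | 0.79 | 57–62% | 1.00 |
| 10% control, 15% intervention | 44% | 0.43 | essentially all | 0.99 |

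With equal coefficients of variation instead, a similar simulation declared non-inferiority in about 62% of runs at 5% per day and 97% at 10% per day.

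**5. Where the effect is small or absent.** With equal stopping and equal SDs, a true slowing of 1.2 days passed in 0% of runs at 10% per day and 15% at 20% per day; a slowing of 1.5 days passed in at most 0.3%. When 40% of diaries were never started, at random, there was no bias (0.97 against 0.97).

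**6. Hazard-ratio scale.** A ratio below 1 means slower recovery on the intervention. At 20% per day, equal stopping and equal SDs, linear imputation gave 0.746 against 0.805 with full data, which is worse for the intervention. With 10% against 15% stopping it gave 0.877 against 0.816, which is better for the intervention.

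**The case against.** The strongest reply is that the SAP never names recovery time as an imputed variable. Continuous app variables also include quality-of-life and pain scores, and for Kaplan-Meier and Cox methods right-censoring is the ordinary treatment of an unfinished diary. This stands as far as it goes: a reader might infer that the trial will give these children a linear-regression recovery time, and the documents do not establish that. Nor do they exclude it. Imputation is the only rule stated for missing app data, no exemption is made, and no censoring rule is written.

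A second reply is that a reader might infer that the rule always hides harm. The documents do not support that either. Protocol 11.1.1 gives a single pooled SD, and with equal SDs and modest, equal stopping the difference in days barely moves. The larger distortions need heavy stopping, unequal stopping or a larger SD in the slower arm, and the documents give no figure for any of these. Unequal stopping cannot be ruled out, since Protocol 8.2 leaves parents unmasked. On the hazard ratio, which is what the SAP reports, the direction can go either way. The SAP also does not say whether the expected drop-out is mostly diaries never started or diaries abandoned part-way, and only the latter leave recorded ill days to contradict.

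A third reply is that censoring is not free of assumptions. If parents stop because the child is well, censoring at the last ill day is informative. This is correct, and the fix has to deal with it.

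**Conclusion.** The point holds as a conflict between a stated imputation rule and the planned survival analysis. Followed literally, the rule produces recovery times that are impossible (14% below 0) or that contradict the diary (38%, 59% and 77% before days 3, 5 and 7). These figures rest only on the protocol's mean and SD and the normality of a linear-regression draw.

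The consequence for the 1-day margin is conditional. Under the assumed gamma model with a true 1-day slowing, the difference in days ranges from almost unchanged (0.94 to 0.98 at 5–10% stopping per day with equal SDs) to roughly halved (0.50 with equal coefficients of variation at 10% per day, or 0.43 with 10% against 15% stopping). It is unaffected if diaries are missing entirely at random, and its direction on the hazard-ratio scale is undetermined. Stopping rates, shape and imbalance between arms are assumptions. The SAP should be changed because the rule is wrong for this outcome whichever scenario applies, and the better method is readily available.

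**What to change.** In the SAP app-data section, exempt time to recovery from the linear-regression imputation and add the following.

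- Define recovery as an explicit diary report of cure. A diary that falls silent without one counts as stopped while ill. The documents do not show the app's items, so confirm that such a report was captured.
- In the Kaplan-Meier, log-rank and Cox analyses, right-censor these children at the last day reported as not recovered, at day 30 at the latest.
- Compare with the 1-day margin using the difference in restricted mean recovery time to day 30, with standard errors that allow for practice clustering. A hazard ratio does not give a difference in days.
- As sensitivity analyses, (a) impute only times beyond the last recorded ill day, from a positive time-to-event distribution, and (b) treat silent diaries as recovered on the day after the last entry.
- Report by arm how many families never started the diary, stopped without reporting cure, and reported cure.

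The cost is SAP wording and some code, with no new data provided the app recorded cure. Intervals will be somewhat wider than with filled-in values. Censoring may be informative if parents stop because the child has recovered; sensitivity analysis (b) addresses that directly, and the counts by arm show how much rests on it.
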